5. GENERAL CONSIDERATIONS

All measures will be summarized descriptively. Continuous variables will be summarized using descriptive statistics such as number of observations (n), mean, standard deviation, standard error, median, minimum, and maximum. Categorical variables will be tabulated using frequency (n) and percent (%).

Unless otherwise specified, the following conventions will be followed in reporting the decimal places.

Reporting Statistics	Decimal Places
Range (Low Value, High Value)	Recorded Decimal Places
Mean, Median	Recorded value + 1 Decimal Places
Confidence Interval, Standard Deviation, Standard Error	Recorded value + 2 Decimal Places
P-value	4 Decimal Places (ex. 0.0021)

The statistical testing will be conducted at a significance level of 0.05 (two-sided) and the 95% confidence interval will be shown, unless specified otherwise. No statistical testing will be conducted for safety measures.

All data manipulations, descriptive summaries, and statistical hypothesis testing will be performed using Statistical Analysis System (SAS) Version 9.4 or later. Individual data, including relevant derived variables, will be listed.

Additional analyses not specified in this SAP may be conducted if deemed necessary and will be documented in the CSR.

5.1. Adjustments for Covariates

Details in covariates to be included in the statistical model for each individual statistical analysis are provided in Section 8.

5.2. Handling of Missing Data

5.2.1. Efficacy Measures

For the analysis of VH 0 response at Month 5 (primary endpoint) and at Month 3 (key secondary endpoint), study eyes will be treated as non-responders if they meet at least one of the following criteria:

- 1. A study eye is rescued due to the protocol-specified worsening of uveitis (Section 8.1.6)
- 2. A subject discontinued from the study due to lack of efficacy or adverse events
- 3. A study eye meets the protocol-specified worsening of uveitis rescue criteria (Section 8.1.6) regardless whether the eye received any rescue therapies

Study eyes which were rescued due to worsening of uveitis specified under previous protocol versions but did not meet the rescue criteria under the current version will be treated as rescued due to other reasons and censored the data after being rescued. The multiple imputation-based approach (Section 8.2.1) will be applied to impute missing VH score data of study eyes which

were not rescued and treated as non-responders. The VH 0 response status will then be determined based on the observed or imputed VH score.

The same approach will be applied to the inferential analyses of other VH response endpoints.

For the analysis of composite score (at Month 3 and at Month 5), study eyes with missing VH score at a given visit will be assigned with a score of 0, unless the study eyes got rescued due to protocol-specified worsening of uveitis or corresponding subjects discontinued the study due to adverse events or lack of efficacy (in this case, the score will be -1).

For the analysis of corticosteroid tapering success on the Intent-to-Taper population, study eyes rescued before Month 5/Month 3 will be treated as corticosteroid tapering failures. The Last-Observed-Carried-Forward (LOCF) approach will be applied to impute missing data of study eyes not rescued before Month 5/Month 3, i.e., the missing overall prednisone-equivalent dose at Month 5/Month 3 will be imputed by last derived overall dose. The tapering status at Month 5/Month 3 will then be determined based on the derived or imputed overall dose.

No imputation is needed for the analysis of the binary endpoint "use of rescue therapy before Month 5/Month 3".

To assess the impact of missing data on the primary analysis results for VH 0 response at Month 5, the following imputation approaches will be applied to some sensitivity analyses:

- The LOCF approach for any FAS study eyes with missing VH score at Month 5
- Treatment policy approach: The primary analysis will be performed on FAS study eyes regardless whether they get rescued. That is, no censoring of observed VH score after a rescue will be implemented. Other missing VH scores will be imputed with multiple imputation-based approach.

For analyses of "change from baseline in central subfield thickness at Month 5 as measured by OCT" and "change from baseline in the NEI VFQ-25 composite score at Month 5", the LOCF approach will be applied for any FAS study eyes with missing score at Month 5.

"Change from baseline in VH score at post-baseline visits up to Month 6" and "change from baseline in BCVA at post-baseline up to Month 6" will be analyzed using the mixed-effects model for repeated measures (MMRM) on observed cases. No imputation of missing data will be needed.

Subgroup analyses of all binary endpoints will employ the same imputation approach for the primary analysis of that endpoint. Other descriptive efficacy summaries will be based on observed data, unless otherwise specified.

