2.2.2. Treatment policy estimand

Vitreous haze (VH) 0 response rate in DE-109 440 μ g group vs. Sham group at Month 5 in all study eyes that received at least one dose of the study treatment regardless of whether subjects have received rescue therapy or discontinued from the study due to lack of efficacy or due to adverse events. For study eyes that had missing data due to any reason, imputation by the multiple imputation-based approach will be used.

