8.2.1. Primary Analyses

The primary efficacy endpoint, VH 0 response, is defined as having a VH score of 0 at Month 5 (modified SUN scale). For the primary endpoint, the VH 0 response rate will be evaluated in accordance with the following null (versus alternative) hypothesis:

$$H_0: \pi_{sham} = \pi_{440}$$
versus

$$H_A: \pi_{sham} \neq \pi_{440}$$

where π_{sham} and π_{440} denote the response rate for sham and 440 µg DE-109, respectively.

The Cochran-Mantel-Haenszel (CMH) test with Row Mean Scores statistic (Yu et al., 2020), stratified by pooled strata based on the number of enrolled eyes from a subject (one eye or two eyes), baseline systemic (oral) corticosteroid use (yes or no), and region (US or non-US). Such pooling is needed to avoid the situation where subjects in too small strata might all have the same responses (either success or failure); hence, do not contribute to the test. To guarantee that

a pooled stratum has at least one success and one failure, the pooling algorithm will be performed as follows:

- Determine the number of subjects in each stratum, defined by crossing the number of enrolled eyes, baseline systemic corticosteroid use, and region.
- Within each combination of number of enrolled eyes and region, if one or both strata, stratified by corticosteroid use, have less than 25 subjects, then those strata will be pooled.
- Within each stratification factor level based on number of enrolled eyes, if at least one of (pooled/unpooled) strata have less than 25 subjects, then those strata will be pooled together.

The pooling algorithm will be performed based on the available data prior to the unmasking of the randomization. At the interim analysis, only number of enrolled eyes will be used as the stratification factor.

Study eyes will be treated as non-responders if they meet at least one of the following criteria:

- 1. A study eye is rescued due to the protocol-specified worsening of uveitis (Section 8.1.6)
- 2. A subject discontinued from the study due to lack of efficacy or adverse events
- 3. A study eye meets the protocol-specified worsening of uveitis rescue criteria (Section 8.1.6) regardless whether the eye received any rescue therapies

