8.2.2. Sensitivity Analyses

The following sensitivity analyses will be performed to assess the robustness of the results from the primary analysis:

- The primary analysis will be repeated on the PP Population.
- The CHM test stratified by the same pooled strata as in the primary analysis will be performed on the FAS population the missing data due to other reasons handled using the Last-Observation-Carried-Forward (LOCF) approach. Subjects who were rescued due to the protocol-specified worsening of uveitis or discontinued from the study due to lack of efficacy or adverse events prior to Month 5 will be treated as non-responders.
- Treatment policy strategy: The CHM test stratified by the same pooled strata as in the primary analysis will be performed on the FAS population regardless whether study eyes get rescued. The missing VH score will be imputed using multiple-imputation approach in the similar manner as described in Section 8.2.1.
- A generalized estimating equation (GEE) method will be used on observed cases up to Month 6 using identity link function. The GEE might be applied on the imputed data (via the same imputation approach as in primary analysis) if there are considerable large amount of missingness. The model will include pooled geographic region (US vs non-US), baseline VH score of the study eye (1.5+, 2+, '3+ or 4+'), treatment, visit, and treatment-by-visit as explanatory variables. An unstructured (UN) correlation structure will be used to model the correlation of the responses from subjects. For subjects rescued before Month 6, all VH scores of study eye collected after the start date of rescue therapy will be excluded from the analysis.
- If the UN correlation structure fails to converge, then an exchangeable (EXCH) correlation structure will be used to model the correlation. If the EXCH model fails to converge, then the independent model will be used.
- Multiple imputation with tipping point analysis will be performed to assess the impact of missing data on the primary analysis results. The following steps will be performed to generate different possible imputation scenarios:

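### The LOCF check of the primary endpoint has different scopes in SAP 5.2.1 and SAP 8.2.2, and 8.2.2 leaves out one of the three non-responder criteria

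*SAP*

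**What the plan says.** SAP 5.2.1 opens with three non-responder criteria for VH 0 response at Month 5 and Month 3, and SAP 8.2.1 repeats them for the primary analysis:

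1. The eye is rescued for protocol-specified worsening.
2. The subject left the study because treatment was not working or because of an adverse event.
3. "A study eye meets the protocol-specified worsening of uveitis rescue criteria (Section 8.1.6) regardless whether the eye received any rescue therapies".

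Protocol 9.5.2 states the third rule generally for the VH response endpoints.

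Further down, SAP 5.2.1 turns to the impact of missing data on the primary result and says that "the following imputation approaches will be applied to some sensitivity analyses". The first approach is "The LOCF approach for any FAS study eyes with missing VH score at Month 5".

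SAP 8.2.2 describes the LOCF analysis again. There LOCF handles only data missing for other reasons. The non-responders before Month 5 are "Subjects who were rescued due to the protocol-specified worsening of uveitis or discontinued from the study due to lack of efficacy or adverse events". Criterion 3 is not mentioned.

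The treatment-policy analysis is also described twice. In SAP 5.2.1, "The primary analysis will be performed on FAS study eyes regardless whether they get rescued", with scores observed after rescue retained. SAP 8.2.2 runs the CMH test with the same pooled strata, regardless of rescue, and imputes missing scores. The estimand in SAP 2.2.2 applies "regardless of whether subjects have received rescue therapy or discontinued from the study due to lack of efficacy or due to adverse events".

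**The concern.** The stated purpose of these analyses is to show how far missing data affect the primary result. That works only if the handling of missing scores is the one thing that changes. If the rule for who counts as a responder changes too, neither agreement nor disagreement with the primary result can be attributed to missing data.

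There are two separate problems. First, the scope of LOCF differs between the sections, so the same eye can be classified differently depending on which one the programmer follows. Second, dropping criterion 3 affects eyes with no missing data at all. An eye can meet a rescue criterion, go without rescue, and still have an observed VH of 0 at Month 5. Two of the three rescue criteria concern visual acuity loss and retinal or choroidal lesions, not haze, and an earlier rise in haze can resolve.

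**Working it through.** **Comparison of the texts.** The table classifies five kinds of eye (R = responder, NR = non-responder). In rows A, B and D the last VH score is 0.

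| Eye | Primary (8.2.1) | 5.2.1 LOCF bullet read alone | 5.2.1 bullet read with the section's opening criteria | 8.2.2 LOCF bullet read literally |
|---|---|---|---|---|
| A. Rescued for protocol-specified worsening, Month 5 missing | NR | R | NR | NR |
| B. Left for lack of efficacy or AE, Month 5 missing | NR | R | NR | NR |
| C. Met a rescue criterion, not rescued, Month 5 observed VH 0 | NR | not covered (score not missing) | NR | **R** |
| D. Met a rescue criterion, not rescued, Month 5 missing for another reason | NR | R | NR | **R** |
| E. Missing for another reason, no criterion met | multiple imputation | LOCF | LOCF | LOCF |

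The check is meant to alter row E only. Rows A and B differ from the primary analysis only if the 5.2.1 bullet is read alone. Rows C and D differ under the literal text of 8.2.2, and row C involves no imputation.

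**Treatment policy.** SAP 2.2.2 disregards rescue and discontinuation for lack of efficacy or AE, which settles criteria 1 and 2. It does not mention eyes that met a rescue criterion without being rescued. SAP 5.2.1 starts from the primary analysis, which contains criterion 3, and lifts only rescue. SAP 8.2.2 restates no non-responder rule. Criterion 3 is therefore left open.

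**Planning figures.** The documents give no figure for the LOCF analysis. The nearest are the planning assumptions in SAP 3.3: 30% vs 12%, 80 subjects per arm, 80% power, two-sided alpha 0.05, Pearson chi-square. These reproduce: 80 per arm without continuity correction, and power 80.4% at 80 per arm.

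**Illustration of sensitivity, not an estimate.** Assumptions: one eye per subject, no stratification, 80 per arm, and 24 vs 10 responders in the primary analysis (30% of 80 = 24; 12% of 80 = 9.6, rounded to 10, or 12.5%). Also assumed is that 0 to 4 eyes per arm are of type C and become responders. The test is z = (p1 − p2) / √[2p̄(1 − p̄)/80], where p̄ is the pooled rate. For 24 vs 10, p̄ = 34/160 = 0.2125, the standard error is 0.0647, and z = 0.175/0.0647 = 2.71.

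| Reclassified DE-109 / sham | Rates | Difference (points) | z | p |
|---|---|---|---|---|
| 0 / 0 | 30.0% vs 12.5% | 17.5 | 2.71 | 0.007 |
| 2 / 0 | 32.5% vs 12.5% | 20.0 | 3.03 | 0.0025 |
| 4 / 0 | 35.0% vs 12.5% | 22.5 | 3.34 | 0.0008 |
| 0 / 2 | 30.0% vs 15.0% | 15.0 | 2.27 | 0.023 |
| 0 / 4 | 30.0% vs 17.5% | 12.5 | 1.86 | 0.063 |
| 2 / 4 | 32.5% vs 17.5% | 15.0 | 2.19 | 0.029 |

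From 22 vs 10 (p = 0.018), two sham eyes give p = 0.053. A few reclassified eyes could move the check either way with the imputation unchanged.

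**The case against.** The best defence is that the documents, read as a whole, already say the right thing. SAP 5.2.1 opens with all three criteria, worded for the Month 5 analysis in general, and introduces the LOCF bullet as an imputation approach. The bullet can fairly be read as saying only how a missing score is filled in. SAP 8.2.2 is the detailed specification and limits LOCF sensibly. Its two-item list may be shorthand: the primary estimand in SAP 2.2.1 names the same two items, yet 8.2.1 still applies criterion 3. LOCF is also one of several sensitivity analyses, and the tipping-point analysis repeats the primary analysis while shifting only imputed values.

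Much of this stands. A reader might infer that neither section keeps the met-criteria rule. The documents do not support that for 5.2.1, where the rule is stated at the start. A reader might also infer that the treatment-policy analysis contradicts its estimand. The estimand settles everything except criterion 3, and only 5.2.1 calls it the primary analysis.

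Two things remain. The wording of 5.2.1 does not favour the charitable reading as clearly as the defence needs. In the same section, LOCF for tapering success is expressly confined to eyes not rescued. The unrestricted phrase used for VH recurs for central subfield thickness and VFQ-25, where no non-responder rules exist. And even on the charitable reading, 8.2.2 still omits criterion 3 without saying whether that is intended.

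**Conclusion.** The LOCF analysis is not uniquely defined. The difference in scope between 5.2.1 and 8.2.2 is on the page, as is the missing criterion 3 in 8.2.2. That 8.2.2 changes a responder rule follows from its literal text. That 5.2.1 does so is only a possible reading.

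No effect size can be given, because the documents report no exit rates and no count of eyes that met a rescue criterion without rescue. The table of p-values rests wholly on assumed counts and shows only that the direction could be either way.

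A reader might infer that LOCF would favour DE-109 by turning adverse-event dropouts into responders. That depends on reading the 5.2.1 bullet alone and on exit rates the documents do not contain. Suppose 10% of DE-109 and 5% of sham eyes exit for lack of efficacy or AE, with VH 0 at the last visit in 12% of the sham exits. The sham rate is then 0.12 + 0.05 × 0.12 = 12.6%. If 10% to 50% of the DE-109 exits had VH 0, the DE-109 rate is 0.30 + 0.10 × (0.10 to 0.50) = 31.0% to 35.0%. The difference is 18.4 to 22.4 points against the planned 18, so the answer is set by the assumption. Protocol 2.3 describes few risks directly related to the 440 µg dose, which gives no basis for presuming such an excess.

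The primary analysis and the hierarchical tests are untouched. The point merits correction because the check is a prespecified support for the primary result and should isolate the imputation.

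**What to change.** Use one LOCF definition in SAP 5.2.1 and 8.2.2: LOCF is applied to FAS study eyes with a missing Month 5 VH score that are not non-responders under any of the three criteria of Section 8.2.1. Add criterion 3 to the non-responder sentence of the 8.2.2 LOCF bullet. Only the imputation then differs from the primary analysis.

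As a secondary edit, state in both treatment-policy bullets that none of the three non-responder criteria is applied, in line with SAP 2.2.2. This closes the gap on criterion 3.

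The cost is wording changes to four bullets, two for LOCF and two for treatment policy, made before unmasking. No new data or additional analyses are needed.

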^a The double-masked period ends with the pre-dose evaluations at Month 6; the first open-label dose of DE-109 is at Month 6.

^b On study visits during the double-masked period at which IP is administered, the unmasked investigator will perform the IP preparation and administration.

^c Signed and dated informed consent form must be obtained prior to conducting any study-related activities.

^d If physical examination and vital signs, VFQ-25 and/or laboratory safety tests were performed at Month 3 under a previous version of the protocol these assessments do not need to be performed at Month 5.

^e Serum and urine pregnancy tests are to be performed on all females of child-bearing potential. Urine pregnancy test (hCG) is to be performed prior to each IP administration. A positive pregnancy test at screening or Day 1 (Baseline) requires exclusion from the study. At subsequent visits, a positive urine pregnancy test requires immediate discontinuation from the study. Pregnancy is an event of special interest and requires follow-up by Santen until the outcome is known.

^f At Month 5 subjects must fast 8 hours prior to the blood draw for hematology and chemistry laboratory tests. At Screening, and Month 12/Exit/Early termination visit, lipid may be obtained in the fasting or non-fasting state.

^g This is only applicable if the subject has consented to collection of blood for pharmacogenomics (approximately 10 mL of blood). This sample should be collected at the Day 14 visit, but may be collected at any time during the study or at a separate post study visit, if necessary.

^h Refer to Section 8.1.3 for assessments and requirements prior to randomization.

ⁱ After IP administration, slit-lamp biomicroscopy is performed first and then indirect ophthalmoscopy, in both eyes within 30 minutes of IP administration.

^j Intraocular pressure (IOP) is measured in both eyes at approximately 40 ± 10 minutes after IP administration. If IOP is increased ≥ 10 mmHg 40 ± 10 minutes after IP administration compared to prior to IP administration, administer topical IOP lowering medication for use until the subject returns for follow-up per the investigator's discretion. (An unscheduled visit may apply). IOP increase of ≥ 10 mmHg at any visit compare to the Baseline (Day 1) assessment should be reported as an AE.

^k Any required blood or urine sample is to be collected before injection of fluorescein.

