Verify that central laboratory results from blood and urine collected at screening have been obtained and reviewed.

Perform the following assessments prior to randomization and prior to administration of IP:

- If the subject is a woman of child-bearing potential, conduct urine pregnancy test. A positive pregnancy test requires exclusion from the study.
- Assess BCVA using ETDRS charts to confirm study eye(s) eligibility (inclusion Section 5.1, #5)
- Administer dilation eye drops (1% Mydriacyl and 2.5% phenylephrine or equivalent applied topically).
- Administer the VFQ-25.
- Obtain fundus photography for immediate submission to reading center.
- Measure IOP.
- Perform slit-lamp biomicroscopy. Assess intended study eye(s) eligibility with respect to VH score ($\geq 1.5+$ in each intended study eye).
- Perform indirect ophthalmoscopy.
- Perform OCT.
- Perform fluorescein angiography (recommended post investigator eligibility confirmation).

- Assess for adverse events.
- Record concomitant medications (including systemic corticosteroid medication status).

Confirm qualifying VH score for each of the subject's intended study eyes has been obtained from the Reading Center based on fundus photography at Day 1. Perform final review of inclusion/exclusion criteria. If the subject and the subject's intended study eye(s) meet all eligibility criteria, randomize the eye(s) into the study using the EDC system (Medidata, including IWRS component) to obtain the assigned vial number(s) to be dispensed to the study eye(s).

The unmasked investigator or designee performs IP preparation and administration as specified in Section 6.2.2 and Section 6.2.3.

Perform the following post IP administration assessments in both eyes:

- Within 30 minutes after the administration of IP:
 - Perform slit-lamp biomicroscopy
 - Perform indirect ophthalmoscopy
- Measure IOP as follows: At approximately 40 (±10) minutes following administration of IP, measure IOP by applanation tonometry. If there is an increase of ≥ 10 mmHg at 40 (±10) minutes post IP administration compared to prior to IP administration, administer topical IOP-lowering drops until the subject returns for follow-up, per the investigator's discretion. (An unscheduled visit may apply). Note that IOP increase of ≥ 10 mmHg should be reported as an adverse event.

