Record the study visit in the EDC system (Medidata) for Month 3.

8.1.8. Double-Masked Treatment Period, Month 4

Allowable visit window: Day 120 ± 3 days; other procedures/details are the same as for Month 2 (Section 8.1.6).

8.1.9. Double-Masked Treatment Period, Month 5

Note: Subjects must fast 8 hours prior to the blood draw for hematology and chemistry laboratory tests taken at Month 5.

Allowable visit window: Day 150 ± 3 days

Visit details:

Perform the following assessments in both eyes:

- Perform physical examination. Note: if this was performed at Month 3 under a previous version of the protocol it does not need to be repeated.
- Record vital signs. Note: if this was performed at Month 3 under a previous version of the protocol it does **not** need to be repeated.

- Collect fasting blood for serum chemistry and hematology tests for laboratory analysis. Note: if these samples were collected at Month 3 under a previous version of the protocol they do **not** need to be repeated.
- Obtain urine sample for urinalysis. Note: if this sample was collected at Month 3 under a previous version of the protocol it does **not** need to be repeated.
- Assess BCVA using ETDRS charts.
- Administer dilation eye drops (1% Mydriacyl and 2.5% phenylephrine or equivalent applied topically).
- Administer the VFQ-25. Note: if this was performed at Month 3 under a previous version of the protocol it does **not** need to be repeated.
- Measure IOP.
- Perform slit-lamp biomicroscopy.
- Perform indirect ophthalmoscopy.
- Obtain fundus photography.
- Perform fluorescein angiography.
- Perform OCT.
- Assess for adverse events.
- Record concomitant medications (including systemic corticosteroid medication status).

Record the study visit in the EDC system (Medidata) for Month 5.

8.1.10. Double-Masked Treatment Period, Month 6

Allowable visit window: Day 180 ± 7 days; other procedures/details are the same as for Month 2

8.1.11. Open-Label Treatment Period, Month 7

Allowable visit window: Day 210 ± 7 days; other procedures/details are the same as for Month 1 (Section 8.1.5).

8.1.12. Open-Label Treatment Period, Month 8

Allowable visit window: Day 240 ± 7 days; other visit procedures/details are the same as for Month 2 (Section 8.1.6).

8.1.13. Open-Label Treatment Period, Month 9

Allowable visit window: Day 270 ± 7 days; other visit procedures/details are the same as for Month 1 (Section 8.1.5).

8.1.14. Open-Label Treatment Period, Month 10

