8.1.16. Month 12/Exit/Early Termination Visit

Allowable visit window for Month 12 visit: Day 360 ± 7 days

Visit details:

Perform the following procedures/assessments in both eyes at Month 12 or at early termination from study if a subject discontinues both study participation and IP after Day 1 and before the Month 12 visit:

- Perform physical examination.
- Record vital signs.
- If the subject is a woman of child-bearing potential, collect blood for serum pregnancy test.
- Collect fasting or non-fasting blood for serum chemistry and hematology tests for laboratory analysis as described in the SoA (Table 3).
- Obtain urine sample for urinalysis.
- Assess BCVA using ETDRS charts.
- Administer dilation eye drops (1% Mydriacyl and 2.5% phenylephrine or equivalent applied topically).
- Administer the VFQ-25.
- Measure IOP.
- Perform slit-lamp biomicroscopy.
- Perform indirect ophthalmoscopy.
- Obtain fundus photography.
- Perform fluorescein angiography
- Perform OCT.
- Assess for adverse events.
- Record concomitant medications (including systemic corticosteroid medication status).

Record the study visit in the EDC system (Medidata) for the Month 12/Exit/Early Termination visit.

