^b On study visits during the double-masked period at which IP is administered, the unmasked investigator will perform the IP preparation and administration.

^c Signed and dated informed consent form must be obtained prior to conducting any study-related activities.

^d If physical examination and vital signs, VFQ-25 and/or laboratory safety tests were performed at Month 3 under a previous version of the protocol these assessments do not need to be performed at Month 5.

^e Serum and urine pregnancy tests are to be performed on all females of child-bearing potential. Urine pregnancy test (hCG) is to be performed prior to each IP administration. A positive pregnancy test at screening or Day 1 (Baseline) requires exclusion from the study. At subsequent visits, a positive urine pregnancy test requires immediate discontinuation from the study. Pregnancy is an event of special interest and requires follow-up by Santen until the outcome is known.

^f At Month 5 subjects must fast 8 hours prior to the blood draw for hematology and chemistry laboratory tests. At Screening, and Month 12/Exit/Early termination visit, lipid may be obtained in the fasting or non-fasting state.

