For each MMRM model, the denominator degrees of freedom for fixed effects will be estimated using the Kenward-Roger approximation (Kenward et al., 1997). An unstructured (UN) covariance matrix will be used to model the within-subject correlation due to study eyes and study visits. If the UN model fails to converge, then an autoregressive of order 1 (AR(1)) covariance matrix will be used to model the within-subject correlation due to study visits while study eye-related within-subject correlation structure remains unchanges. If the AR(1) model fails to converge, then the compound symmetry model will be used.

The following secondary endpoints will be analyzed using the analysis of covariance (ANCOVA) with missing data at Month 5 being imputed by the LOCF approach:

- Change from baseline in CST at Month 5 as measured by OCT
- Change from baseline in the NEI VFQ-25 composite score and subscales at Month 5

For the analysis of change from baseline in CST at Month 5, the ANCOVA model will include study eye, country (US or non-US), baseline systemic (oral) corticosteroid use status, and treatment as factors and baseline CST score as a covariate. Correlations of change from baseline in CST within a subject due to eyes will be modeled using UN structure.

For the analysis of changes from baseline in the NEI VFQ-25 composite score and subscales at Month 5, the ANCOVA model will include country (US or non-US), baseline systemic (oral) corticosteroid use status, baseline VH score of the study eye (1.5+, 2+, or '3+ or 4+') or the worse study eye (i.e., higher VH score) for subjects who enrolled both eyes, number of enrolled study eyes, and treatment as factors and baseline VFQ-25 score as a covariate.

For each of these continuous endpoints, the least squares (LS) mean change from baseline of each DE-109 group with its standard error will be reported. For each treatment comparison, the LS mean difference with the 95% CI will be reported.

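### LOCF for a missing Month 5 VFQ-25 has no Month 5-like score to carry: under the current schedule it inserts zero change or a score from another time point

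*SAP*

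**What the plan says.** **Imputation.** SAP 5.2.1 covers two endpoints in one sentence, change in CST and change in VFQ-25 composite score at Month 5, and states that "the LOCF approach will be applied for any FAS study eyes with missing score at Month 5". SAP 8.2.4.2 places "Change from baseline in the NEI VFQ-25 composite score and subscales at Month 5" under ANCOVA "with missing data at Month 5 being imputed by the LOCF approach".

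**Schedule.** The VFQ-25 appears at three points in the schedules of activities (Protocol 1.3, SAP 3.4): Day 1, Month 5, and Month 12/Exit/Early Termination.
- Day 1 (Protocol 8.1.3): the pre-dose list includes "Administer the VFQ-25".
- Month 3 (Protocol 8.1.7): no VFQ-25 in the current version.
- Month 5 (Protocol 8.1.9): "Administer the VFQ-25. Note: if this was performed at Month 3 under a previous version of the protocol it does" not need repeating. Footnote d of the Protocol schedule gives the same exemption where "VFQ-25 and/or laboratory safety tests were performed at Month 3 under a previous version of the protocol", and SAP 3.4 repeats it.
- Exit (Protocol 8.1.16): the procedures, VFQ-25 included, apply "at Month 12 or at early termination from study if a subject discontinues both study participation and IP after Day 1". Protocol 7.2 makes the early-termination visit conditional on its being possible.

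**Related rules.** SAP 4.3 equates the analysis visit with the nominal visit. Protocol Table 8 assigns change-from-baseline secondary endpoints to an observed-case MMRM. SAP Section 10, which lists changes to the protocol, does not mention LOCF ANCOVA. The sensitivity analyses in SAP 8.2.2 concern the primary endpoint only.

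**The concern.** LOCF needs a post-baseline score taken reasonably close to the missing visit. The VFQ-25 has no scheduled post-baseline score before Month 5. A subject who stays in the study but misses the Month 5 questionnaire, and has no Month 3 score, has only Day 1 to carry, and the change is then zero by construction. A subject excused because of a Month 3 test is missing by design, and the Month 3 score is analysed as if it were Month 5. Month 3 follows two administrations (Day 1, Month 2); Month 5 follows three.

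At stake is the estimated treatment difference in the trial's patient-reported outcome. Zero-filling shrinks the mean change in each arm in proportion to the share filled. Where that share differs between arms, the estimate can move in either direction, including away from zero when there is no effect. With no VFQ-25 sensitivity analysis planned, the LOCF result would be the only model-based one.

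**Working it through.** **Plan figures.** The documents give no VFQ-25 effect size, SD, sample size or missing rate, so there is no VFQ-25 figure to reproduce. The only sample-size figure (SAP 3.3: 80 per arm, 30% v 12%, 80% power, two-sided 0.05) is for VH 0 response. It reproduces: the pooled two-proportion formula gives 80 per arm and 80.4% power. It does not bear on this point.

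**Step 1: which score can be carried.** Setting the LOCF rule beside the schedule leaves three sources.

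| Subject with no Month 5 VFQ-25 | Last score available | Consequence |
|---|---|---|
| Stayed in the study with no Month 3 score, or left with neither a Month 3 nor an early-termination score | Day 1 | Change exactly 0, if baseline may be carried |
| Tested at Month 3 under an earlier version and excused | Month 3 | A Month 3 change analysed as Month 5 |
| Left before Month 5 and attended the early-termination visit | That visit | Change at the time of leaving, analysed as Month 5 |

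Because analysis visits are nominal visits, no other rule maps a Month 3 or early-termination score to Month 5; LOCF alone does so.

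**Step 2: effect of carrying baseline.** Let f be the share of an arm with baseline carried and m the mean change in the remaining subjects. The arm's mean change becomes m × (1 − f) + 0 × f = m × (1 − f). With equal f in both arms, the difference is multiplied by (1 − f): 0.95, 0.90, 0.80 and 0.70 for f of 5%, 10%, 20% and 30%.

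**Step 3: worst case.** Assume that every missing subject has baseline carried, so f is the whole missing share. Assume mean changes of 13 (DE-109 440 µg) and 8 (sham), a true difference of 5. The means and missing shares are assumptions.
- 10% and 10%: 13 × 0.90 − 8 × 0.90 = 11.70 − 7.20 = 4.50
- 5% active, 15% sham: 13 × 0.95 − 8 × 0.85 = 12.35 − 6.80 = 5.55
- 15% active, 5% sham: 13 × 0.85 − 8 × 0.95 = 11.05 − 7.60 = 3.45
- No true effect (8 in both arms), 5% active, 15% sham: 8 × 0.95 − 8 × 0.85 = 7.60 − 6.80 = 0.80

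These are differences in unadjusted means. Each Month 3 or early-termination score that is carried takes a subject out of f and reduces this effect, but adds an error from the different time point. The documents give nothing from which to size that error.

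**The case against.** Several stronger readings are tempting, and the documents do not support them.

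- **Every missing score becomes zero change.** A reader might infer this from the rule's reference to any missing score. The early-termination visit includes the VFQ-25, so some leavers have a real post-baseline score. The SAP also never says that baseline may be carried. If only post-baseline scores qualify, the affected subjects drop out of the ANCOVA and no zero is inserted. This limits how often zero-filling occurs, but the literal wording still permits it, and the alternative is equally unstated.
- **Constant imputed values must understate the variance.** This does not hold in general. With a mean of 13 and 10% zeros, the variance of raw change is 0.9 × SD² + 0.09 × 169, which exceeds SD² whenever SD is below about 12.3. The documents give no VFQ-25 SD.
- **CST has the same defect.** It shares the sentence, but OCT is done at every visit from Day 1, so a recent post-baseline value normally exists.
- **The rule is written for the wrong unit.** It names study eyes, yet SAP 6.2 defines the FAS by subject for per-subject parameters, and the VFQ-25 model in SAP 8.2.4.2 is subject-level. This is a wording slip.
- **The SAP contradicts the protocol.** Table 8 states a general method, but the VFQ-25 change is not among the endpoints listed there; the SAP adds it, as the protocol allows. What stands is that the SAP departs from the general observed-case approach without recording it in Section 10.

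Stakes are also modest. Protocol Table 8 calls the other secondary endpoints supportive, and the VFQ-25 is outside the hierarchy in SAP 5.4. Descriptive efficacy summaries default to observed data, so observed-case means should be visible, although no observed-case ANCOVA is planned.

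**Conclusion.** The concern holds for the VFQ-25 alone. Applied as written, LOCF supplies the Month 5 analysis with zero change or with a score from another time point, never with a Month 5 value. In the worst case above, a true difference of 5 is reported as anything from 3.45 to 5.55, and a null effect as 0.8. Those figures rest on assumed mean changes, assumed missing shares of 5% to 15%, and baseline carried for every missing subject; the actual effect depends on rates that the documents do not give. A reader might infer that the trial's main result is at risk. It is not: the endpoint is supportive and outside the alpha hierarchy. The point is still more than missing detail, because a stated rule yields a biased estimate with no sensitivity analysis to show it, and a better analysis is available from data already collected.

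**What to change.** For the VFQ-25 only, leaving CST as it is:

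1. Replace LOCF with a subject-level Month 5 ANCOVA using multiple imputation under MAR by arm. Use as predictors baseline VFQ-25, the model covariates, and BCVA and VH through Month 5. For two-eye subjects take the worse study eye, as the SAP 8.2.4.2 model already does for baseline VH.
2. Do not carry baseline forward.
3. Keep Month 3 scores labelled as Month 3 and report how many subjects have only a Month 3 score. Use the Month 3 VFQ-25 as a predictor only if enough subjects have both scores; few or none may, because the Month 3 test is what excused them at Month 5.
4. Report the observed-case ANCOVA as a sensitivity analysis.
5. In SAP 5.2.1, change study eyes to subjects for the VFQ-25, and record the chosen method in SAP Section 10.

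The cost is SAP wording, a small extra imputation step and possibly a wider confidence interval. No new data are needed. For subjects with only a Month 3 score, the imputed value will rest on modelling assumptions, which is why their number should be reported.
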